7.4 Source Data

The investigator/institution should maintain adequate and accurate source documents and trial records that include all pertinent observations on each of the site's trial participants. Source data are contained in source documents and are defined by guidelines as all information in original records that are used for the reconstruction and evaluation of the clinical trial. Source documents are the first place where the source data are recorded.

Source data should be attributable, legible, contemporaneous, original, accurate, and complete. Changes to source data should be traceable, should not obscure the original entry, and should be explained if necessary (e.g., via an audit trail). Each data element should only have one source.

For this trial, the CRFs/eCRFs will be the source document for the data elements listed below. These data elements will be recorded directly on the CRFs/eCRFs and therefore the CRFs/eCRFs will be regarded as source data. On occasions a research assistant might enter some data on behalf of the participant:

- *Participant questionnaires*
- *Cognitive assessments*
- *Treatment compliance data*
- *Trial Management Data*

7.5 Data Collection and Transfer Methods

Training on data collection, secure data transfer and storage for site staff listed on the delegation of responsibilities log will be provided at the site initiation meeting(s) and whenever someone new is added to the delegation log.

7.6 Data Management

Data will be collected at the time-points indicated in the Participant Timeline (Section 5.1). Data will be entered under this PIN onto the central database. The database software provides a number of features to help maintain data quality, including maintaining an audit trail, allowing custom validations on data, allowing users to raise data query requests, and search facilities to identify validation failure and missing data.

Data collection, data entry, queries raised by a member of the PETRA trial team and database lock(s) will be conducted in line with the CCTU SOPs and trial-specific Data Management Plan.

The database will be password protected and only accessible to members of the PETRA trial team at UCL, Bristol and Keele; delegated site staff and external regulators if requested. Database users will only be granted permissions to use the database functionality appropriate to their role in the clinical trial.

Identification logs, screening logs and enrolment logs will be completed and held securely with access limited to trial staff that require the information.

All data will be handled in accordance with the Data Protection Act 2018, the EU General Data Protection Regulation (GDPR) 2016 (and subsequent updates and amendments).

7.7 Data Storage

Trial data will be stored in a database created specifically for the PETRA trial.

The database is hosted by OpenClinica. The data are stored on secure, GDPR-compliant, cloud-based servers held within UK and EU: <https://www.openclinica.com/privacy-policy/>

The randomisation service is hosted by Sealed Envelope LTD. The data are stored on a secure, GDPR-compliant, cloud-based servers held within the EU: <https://www.sealedenvelope.com/security/>

The identification, screening and enrolment logs, linking personally identifiable information to the PIN, will be held securely in the UCL Data Safe Haven with access given to essential staff only. After completion of the trial the identification, screening and enrolment logs will be stored securely by the sites and the Keele University co-ordinating centre for 5 years after trial closure unless otherwise advised by CCTU.

7.8 Data Archiving

Once all primary and secondary analysis has been completed the trial data will be archived. Once the trial data has been archived the trial database will be decommissioned and will no longer be available. Any subsequent/ further analysis will be performed using the archived data.

7.9 Quality Issues

Quality Issues are issues that can have an impact on patient safety, rights, and well-being; data integrity and/or scientific rigor; and compliance with regulatory requirements; these can be classified as protocol deviations, potential serious breaches, near misses etc.

A protocol deviation is any departure from procedures documented in this protocol, this includes deviations that cannot be predicted. If a protocol deviation is identified the Trials team should be contacted and CCTU's protocol deviation reporting process will be followed.

A 'serious breach' is a deviation from procedures documented in this protocol, GCP or other clinical trial regulations that is likely to affect to a significant degree:

1. The safety or physical or mental integrity of the participants in the trial, or
2. The scientific value of the trial.

If a serious breach is suspected the Sponsor must be contacted within 1 working day. In collaboration with the CI, the serious breach will be reviewed by the Sponsor and, if appropriate, the Sponsor will report it to the REC committee and/or Regulatory authority (MHRA) within 7 days.

8 Statistical Considerations

8.1 Sample Size

We have estimated the minimal clinically important difference for the GAD7 as about a 20% reduction (Kounali *et al.*, 2020). From the Cobalt and MiR results at 6 months our MCID estimate is 1.6 or 1.9 GAD7 points and standard deviations (SDs) were 5.6 or 5.8. In those trials the correlation between baseline and 12-week GAD7 scores was 0.47 so this leads to an effective SD of 4.9. For a difference of 1.6 GAD7 points we need 199 per group for 90% power at the 5% significance level. Our target is 498 allowing for 20% attrition or other methodological challenges at 12 weeks, though we would expect to achieve substantially better follow up. For the withdrawal study, the power depends upon the position on the binomial distribution, but clinically important differences in withdrawal effects will be detectable. For example, we will have 85% power to find a difference between the groups where the control condition has a proportion of 2.5% of withdrawal symptoms and the pregabalin group 10%.

8.2 Assignment of Intervention

8.2.1 Randomisation Procedures

A PIN will be allocated to participants before the Screening assessment, the PI or delegate will enter the necessary participant characteristics required to uniquely identify each participant. Delegated staff will be provided with a secure login to the SealedEnvelope.com website, according to their role in the trial. The randomisation result will be sent directly to the distribution pharmacy. The Trial team will not know the allocation but will be informed that the randomisation has occurred.

8.2.2 Randomisation Method

We will use a web-based computerised system to randomise with a 1:1 ratio, using a minimisation procedure to achieve balance between minimization groups. Minimisation groups will be specified in the Statistical Analysis Plan and in the randomization and minimization document for Sealed Envelope.

8.2.3 Sequence generation

The minimisation procedure will use a 70:30 'biased coin' procedure to asymptote towards balance while including a random element in each allocation. It will be provided by Sealed

Envelope (<https://www.sealedenvelope.com/>) under the supervision of UCL Comprehensive Clinical Trials unit, CCTU (<https://www.ucl.ac.uk/comprehensive-clinical-trials-unit/>).

8.2.4 Allocation concealment mechanism

Randomisation will be concealed by using a remote computerised system and the pharmacy will be directly informed of the randomisation outcome. The active and placebo drug will be identical in appearance and researchers, clinicians and participants will be blind to allocation. A participant will be considered randomised at the point that they take their first IMP, and participants returning their untampered IMP will not be considered to have been randomised and thus will not be listed as lost to follow up.

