Recruitment rate/region /month	4 randomisations per month	6	8
Number of GP practices opened	8	11	16
Total number of participants recruited	24	36	48

In addition to the recruitment targets given above, we will set a target of 90% for participants starting study medication, 80% for completing follow up assessments at the primary endpoint and as a measure of acceptability, we will require 70% of the participants to be taking study medication at the primary outcome assessment at 12 weeks. This will be reviewed at the end of the pilot and results presented to the Trial Steering Committee and Data Monitoring Committee.

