8.2.5 Allocation Implementation

Once informed that an eligible participant has been identified and has consented to enter the trial, the random allocation of the participant to medication will be done by Sealed Envelope (<https://www.sealedenvelope.com/>). Analyses will be carried out to ensure that the randomisation procedure was successful in producing equal groups for each of the specified minimisation criteria. The procedure is unpredictable as the minimisation allocation will employ a 70:30 “biased coin” to asymptote towards equality which ensures an element of randomness in each allocation.

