8.3.3 Statistical Methods – Outcomes

The primary analysis will be a generalised mixed model with identity link and Gaussian / mixed error structures, with log(e) GAD7 scores at 12 weeks as the outcome, accounting for baseline GAD7 scores using a repeated measures framework and also including minimisation factors used in the randomisation process. Natural logarithms will be used following our previous experience with the PANDA study(Lewis *et al.*, 2019) that suggested it was more efficient, and evidence that minimal clinically important differences for scales such as GAD fit a geometric model more closely. There will be two observations for each participant, the baseline and 12-week scores. These will be linked within a participant using a random intercept term. The model will be parameterised to identify baseline and post randomisation observation as one parameter, and random allocation as the second parameter. For the latter, all baseline measures will be coded as no treatment, and the post randomisation values will be classified as active or placebo. We will not make adjustments for repeated testing but will discuss the possibility that type 1 errors would have increased in the discussion.

Secondary analyses will choose the appropriate analogous generalised mixed model, for the outcome and account for the baseline measurement of the outcome. We will describe randomised groups at baseline. Summary statistics for continuous variables will be mean, median, SD, lower quartile, upper quartile and reported appropriately according to distribution. Summary statistics for binary and categorical variables will be n (%).

We will carry out supportive analyses including the minimisation variables as explanatory variables. We will also investigate baseline variables associated with missing outcome data for the primary outcome. We will carry out mediation analyses to examine the influence of missingness. All principal analyses will be complete case, intention to treat (defined as all patients randomised, analysed according to their randomised group regardless of treatment received). Although we will minimise missing data by trial conduct (building on the considerable experience and success of the team on previous studies) we will investigate the potential impact of missing data on the primary objective through threshold analyses which will impute a poor outcome for missing pregabalin patients while assuming an average outcome for missing control patients.

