8.3.6 Analysis Population and Missing Data

Outcomes will be analysed by means of Generalised Mixed Models without imputation of missing data. Measurements within individuals will be linked using a random intercept term. We will use two timepoints for the final analysis; baseline and primary timepoint at 12 weeks. An Intention-To-Treat (ITT) analysis will be carried out by randomisation group irrespective of medication compliance. The analysis population will consist of all those participants who were randomised. Mechanisms of missingness will be explored. The principal analyses will address a treatment strategy estimand, except death which will be while alive.

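### Counting participants as randomised only from their first tablet turns the intention-to-treat set into an at-least-one-dose set and overstates follow-up relative to those allocated

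*Protocol*

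**What the plan says.** The protocol gives two accounts of when randomisation happens.

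- **At web allocation.** Section 8.2.5 says that "the random allocation of the participant to medication will be done by Sealed Envelope" once an eligible person has consented. Section 8.2.1 sends the result straight to the pharmacy and says that the trial team "will be informed that the randomisation has occurred". Both steps come before any tablet can be taken.
- **At first intake.** Section 8.2.4 says that "A participant will be considered randomised at the point that they take their first IMP", and adds that "participants returning their untampered IMP will not be considered to have been randomised and thus will not be listed as lost to follow up".

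The analysis sections build on the word randomised. Section 8.3.3 describes the principal analyses as "intention to treat (defined as all patients randomised, analysed according to their randomised group regardless of treatment received". Section 8.3.6 says: "The analysis population will consist of all those participants who were randomised", with compliance playing no part.

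For the internal pilot, section 3.3 says "we will set a target of 90% for participants starting study medication". It also sets 80% for follow-up at the primary endpoint and 70% for being on study medication at 12 weeks. None of the three has a stated denominator. Table 2 in the same section expresses the monthly recruitment rate in randomisations.

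**The concern.** An intention-to-treat set keeps everyone to whom chance assigned a treatment, whatever they then did. Here, whether a person belongs to the set depends on something that happens after allocation, namely taking a tablet. The sentence defining ITT reads correctly on its own, but combined with 8.2.4 it describes a different population from the one its label promises.

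Three reported quantities are affected:

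1. The analysis set would be published as ITT when it is a modified ITT set.
2. Follow-up would be a percentage of starters and would look better than the percentage of those allocated.
3. The pilot target for starting medication may have a denominator made up only of people who started.

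The protocol fixes this rule itself, so it is not a detail left to the statistical analysis plan.

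**Working it through.** **1. The plan's own sample size (section 8.1).** Inputs: difference 1.6 GAD7 points, effective SD 4.9, 90% power, 5% significance (two-sided assumed).

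- n per group = 2 × (1.960 + 1.282)² × 4.9² / 1.6² = 197.1, rounded up to 198. The protocol states 199, and power at 199 per group is 90.3%.
- Total after 20% attrition: 2 × 199 / 0.80 = 497.5, rounded up to 498, as stated.

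The sample size reproduces.

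**2. Who is in the analysis set.**

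| Person | Allocated (8.2.1, 8.2.5) | Randomised (8.2.4) | In the ITT set (8.3.3, 8.3.6) |
|---|---|---|---|
| Takes at least one tablet, then stops | yes | yes | yes |
| Returns the supply unopened | yes | no | no |
| Takes nothing, does not return the supply | yes | no, by the first-intake rule | no |

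The second and third rows are removed after allocation because of the treatment they received.

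**3. Effect on reported follow-up.** Let s be the share of allocated people who never take a tablet. The protocol gives no value, so 5%, 10% and 20% are assumptions. Assume also that never-starters are not followed up.

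- Follow-up among allocated = follow-up among starters × (1 − s)
- Follow-up among starters = follow-up among allocated / (1 − s)

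| s | 80% of starters, as a share of allocated | 80% of allocated, as it would be reported |
|---|---|---|
| 5% | 0.80 × 0.95 = 76% | 0.80 / 0.95 = 84% |
| 10% | 0.80 × 0.90 = 72% | 0.80 / 0.90 = 89% |
| 20% | 0.80 × 0.80 = 64% | 0.80 / 0.80 = 100% |

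**4. What 498 counts.** Under 8.2.4 as written, 498 randomised people are 498 starters. The web system would then have to allocate 498 / (1 − s) people: 525, 554 or 623 for s of 5%, 10% or 20%.

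**5. The pilot targets (section 3.3).** Take 48 allocated people, the number in the green column of Table 2.

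| s | Starters | Share of allocated | Share of randomised (8.2.4) |
|---|---|---|---|
| 10% | 43 | 43/48 = 89.6% | 43/43 = 100% |
| 15% | 41 | 41/48 = 85.4% | 41/41 = 100% |
| 20% | 38 | 38/48 = 79.2% | 38/38 = 100% |

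With randomised participants as the denominator, the start rate is 100% for every s. The 70% on-medication target shifts in the same way as follow-up: at s = 10%, 70% of starters is 0.70 × 0.90 = 63% of those allocated.

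**The case against.** The strongest defence is that the rule is stated openly and does little harm to the comparison. Allocation is concealed and the tablets and bottles are matched (8.2.4, 8.2.6), so a person who has taken nothing has no obvious way of knowing their arm. Non-starting should then be unrelated to arm. People who start and later stop are still invited to every assessment (4.2.4) and analysed as randomised. Section 8.2.4 says only that those returning unopened supplies are not listed as lost; it does not say that they vanish from the participant flow. All of this stands, and it limits the point to labels and denominators.

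Four stronger readings are tempting but not supported:

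- **The 90% target is met by definition.** Section 3.3 names no denominator. If everyone allocated is meant, the target can fail, but it then rests on a count that 8.2.4 does not recognise as randomised. The finding is that the two sections need reconciling. The target is also not among the four primary criteria listed in 8.3.2.
- **Someone who keeps the bottle unused stays in, while someone who returns it drops out.** The first-intake rule excludes both. What 8.2.4 leaves open is how intake is verified when the supply does not come back.
- **Power falls to about 87%.** That figure needs 498 to mean allocations and an assumed 10% non-start on top of 20% loss (498 × 0.9 × 0.8 / 2 = 179 per arm). Under 8.2.4 the 498 are starters, and the 20% in 8.1 already covers other methodological challenges as well as attrition.
- **Serious events are missed because reporting runs from randomisation (6.3.2.1).** Sections 6.1 and 6.1.2 define adverse events as arising after the product is given, so starting the clock at first intake loses none that qualify.

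**Conclusion.** The point holds as a wrong label and a wrong denominator. By the protocol's own definitions, the population called ITT is an at-least-one-dose set, and follow-up relative to those allocated is overstated by 1/(1 − s). At the assumed non-starter shares of 5%, 10% and 20%, a reported 80% corresponds to 76%, 72% and 64% of those allocated, provided never-starters are not followed up. The true share is unknown, and if it is close to zero the effect is negligible.

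The documents do not support a claim that the treatment estimate is materially biased: blinding makes that unlikely, though a post-allocation exclusion cannot rule it out. They also do not support a claim that the sample size is wrong. The pilot start target is either unable to fail or inconsistent with 8.2.4, depending on a denominator that section 3.3 does not state. The text should be corrected, but the design is not undermined.

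**What to change.** 1. In 8.2.4, define randomisation as the moment the web system issues the allocation, and delete the sentence tying it to first intake.
2. Keep every allocated participant in the ITT set, the participant flow and the follow-up denominators. Invite never-starters to the assessments, as those who stop treatment already are.
3. Report the number who never started, by arm, and say how first intake is established when the supply is not returned.
4. If an at-least-one-dose set is wanted, name it a modified ITT or safety set.
5. In 3.3, state that the 90%, 80% and 70% pilot targets are measured against all allocated participants.

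The cost is wording changes, follow-up attempts for a few non-starters and slightly lower reported retention. If never-starters supply 12-week scores and have no drug effect, the ITT contrast becomes (1 − s) times the contrast among starters. That is what the treatment-policy approach in 8.3.1 and 8.3.6 sets out to measure, and a modified ITT analysis can be shown beside it.

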8.2.5 Allocation Implementation

Once informed that an eligible participant has been identified and has consented to enter the trial, the random allocation of the participant to medication will be done by Sealed Envelope (<https://www.sealedenvelope.com/>). Analyses will be carried out to ensure that the randomisation procedure was successful in producing equal groups for each of the specified minimisation criteria. The procedure is unpredictable as the minimisation allocation will employ a 70:30 “biased coin” to asymptote towards equality which ensures an element of randomness in each allocation.

8.2.6 Blinding

This will be a double-blind designed trial. Investigators, research teams at sites and the Keele University co-ordinating centre, participants, the trial team at UCL and the blinded trial statistician will be masked to treatment allocation. The only exception being the delegated unblinded trial statistician, the third-party IMP licensed manufacturing facility and distribution pharmacy, unblinded monitor who will monitor the pharmacy and SUSAR reporting team (independent of trial team) at CCTU.

Blinding will be maintained by using matching medicinal preparation for pregabalin and placebo (matched size/appearance, taste of tablets and identical bottles). The blinded treatment identity will be maintained in the online Sealed Envelope randomisation service except in the case of medical emergency (see 4.6.1 Emergency unblinding).

As the study is double-blind and the active drug and placebo will be of identical appearance, any change in the number of tablets will not in any way affect the blinding. Neither the participant, research assistant, PI or GP will know whether the participant is taking active or placebo and this will be impossible to find out without asking the pharmacy to “unblind”.

8.3 Statistical Considerations

8.3.1 Estimand Framework & Statistical Analysis Plan

Table 5. Estimand Framework

Characteristic of estimand	Definition and method of analysis
Population	Participants who have a diagnosis of generalised anxiety disorder, who have not responded to at least two antidepressant

	medications, who are currently still taking antidepressant medication, who are in the community, who agree to enter the trial and who do not fulfil exclusion criteria.
Treatment conditions	Pregabalin medication versus placebo in addition to care as usual
Endpoint	Natural log of the score on the Generalised Anxiety Disorder scale at 12 weeks post randomisation
Summary measure	Mean difference between natural log of the score on the Generalised Anxiety Disorder scale at 12 weeks post randomisation between those randomised to placebo versus those randomised to pregabalin (adjusting for baseline scores).
Intercurrent Events	
 i. Death before outcome While alive policy ii. Withdrawal from randomised medication (stays in trial) Treatment policy iii. Withdrawal from medication (leaves trial) While in trial policy iv. Increased use of alcohol Treatment policy v. Psychiatric admission Treatment policy vi. Commencement of psychological therapies Treatment policy

Statistical Analysis Plan

A separate Statistical Analysis Plan will be pre-specified which will be held within the Statistics Master File (SMF). It will contain following sections:

- I. Introduction
- II. Study Methods
- III. Statistical Principles
- IV. Trial Population
- V. Analysis of Primary and Secondary Outcomes (including statistical models and method of dealing with missingness)

